### *Sensitivity Analysis*

Secondary endpoints will be assessed for alternative definitions of treatment arm. Analyses will mirror the primary analysis of secondary endpoints, replacing the treatment arm with the following alternative definitions:

1. Metformin 1500mg ER vs. Metformin 1000mg ER vs. Metformin 500mg ER vs. Placebo (each pooled across duration) (Primary Approach)
2. Long Metformin (>90 days) vs. Medium Metformin (29-90 days) vs. Short Metformin (7-28 days) vs. Placebo (each pooled across the 3 doses of study drug)
3. Placebo vs. 500mg and 7-28 day duration vs. all other treatment combinations

Model structures will mirror the primary analysis of secondary endpoints and statistical significance

will again be defined as an unadjusted  $p < 0.025$ .

### **13.2.1. Descriptive Statistics for Secondary Dichotomous Endpoints**

In addition to models described above, dichotomous, categorical, and time-to-event endpoints will be reported using descriptive statistics, including number and percent, overall and by strata, as described above in Section 11. Results will be stratified by the definition of treatment used in the primary analysis of secondary endpoints (i.e., treated vs. untreated) only.

### **13.3. Subgroup Analyses**

For the primary outcome of HFD-90 only, subgroups will be evaluated using a frequentist cumulative logistic regression model, as in the primary analysis. These analyses will be conducted on both the ITT and PPA populations and will follow the same approach to pooling across duration and borrowing across dose as in the primary analysis. Analyses will be stratified by each of the following subgroups:

1. Age >= overall median vs < overall median (hypothesis, more effective among those > median)
2. Sex at birth (hypothesis: no difference)
3. Frailty, comparing robust/normal vs. frail/very frail (hypothesis, more effective among frail and very frail). Note that subgroup of robust with normal and frail with very frail may be modified as necessary (e.g., to robust vs. normal/frail/very frail) if sample size for either group is <= 25).
4. Surgical strata (hypothesis, no difference)
  - o No operation
  - o Spine
  - o General surgery/surgical oncology
  - o Colorectal Surgery
  - o Other
  - o Any strata with <= 25 subjects will be combined into the "Other" category, except the "No operation" group
5. Surgical stress (hypothesis, more effective among higher stress procedures)
  - o Same day surgery procedures
  - o Procedures with subsequent hospital admission

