## 13. ANALYTIC APPROACH

Primary inferential analyses will be done using a Bayesian approach. Sensitivity analyses will be conducted using both Bayesian and Frequentist approaches, as described. Secondary endpoints will be analyzed using frequentist approaches. A summary of the analyses methods is provided below. For all frequentist models, statistical significance will be defined as a one-sided p-value of <0.025, and for all Bayesian models a one-sided posterior probability > 0.975. If stable inference cannot be made due to sparseness of data within strata/categories, data may be further collapsed as needed.

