### 13.1. Primary Analysis of Primary Endpoint

#### *Primary Analysis*

The **primary analysis model** is a Bayesian cumulative logistic model for the ordinal primary endpoint. The primary analysis is to be completed in both the ITT and PPA populations described above.

In the primary analysis, observations will be pooled across pre-operative duration of study drug and will borrow across study drug dose. The primary endpoint for this model is HFD-90 and will be compared across the placebo and three levels of study drug dose. The general Bayesian cumulative logistic model is defined below:

Throughout we assume for patient  $i$ ,  $y_i$  is the observed 90-day HFD,  $g(i)$ , is the surgical strata from 1:G,  $d(i)$  is the pre-op duration from 1:3 with 1 = short, 2 = intermediate, and 3=long, and  $t(i)$  is the intervention from 1:4 with 1 = placebo, 2 = 500mg, 3 = 1000mg, and 4 = 1500mg.

The general Bayesian ordinal logistic regression model is used to estimate the effect of dose and duration of metformin on the distribution of HFD-90 under placebo adjusting for expected differences given the surgical strata. The ordinal scale parameterization is a generalized version of the dichotomous parameterization where we model all cumulative probabilities of 90-day HFD being less than or equal to a cutpoint  $c$ , where  $c = -1, \dots, 89$ . Given each cutpoint  $c$ , we denote the 91 dichotomized versions of 90-day HFD for patient  $i$  as  $\gamma_{c,i}$  where  $\gamma_{c,i} = 1$  if 90-day HFD is in  $[-1, c]$  and  $\gamma_{c,i} = 0$  if 90-day HFD is in  $[c+1, 90]$  for  $c = -1, \dots, 89$ .  $\gamma_{c,i}$  is then modeled throughout as:

$$\gamma_{c,i} \sim \text{Bernoulli}(\phi_{c,i});$$

$$\text{logit}(\phi_{c,i}) = \gamma_c + \mu_i;$$

where  $\mu_i$  is a patient-specific mean function and  $\gamma_c$  is common across all patients. To assure model stability, if there is an outcome in the ordinal scale that did not occur in the data, then that outcome will be combined with a neighboring outcome (the worse outcome). For example, if the outcome 11 never occurred, then a combined outcome of 10 & 11 will be modeled for the analysis.

The subject-specific mean function is as follows:

$$\mu_i = \alpha_{g(i)} + \theta_{t(i), d(i)}.$$

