### **13.6. Multiple Comparisons**

No adjustment for multiple comparisons will be made, as the primary analysis model is for a single endpoint and secondary endpoints are intended to provide a broad statistical context for results of the primary analysis model.

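### SAP 13.3: about 10 to 12 subgroup levels are each open to a one-sided p<0.025 label on HFD-90, with no exploratory status, no interaction test and no mention in the multiplicity section

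*SAP*

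**What the plan says.** - **Model (SAP 13.3).** "For the primary outcome of HFD-90 only, subgroups will be evaluated using a frequentist cumulative logistic regression model, as in the primary analysis".
- **Populations (SAP 13.3).** "These analyses will be conducted on both the ITT and PPA populations".
- **Dose and duration (SAP 13.3).** The analyses "will follow the same approach to pooling across duration and borrowing across dose as in the primary analysis". In the primary analysis (SAP 13.1), HFD-90 "will be compared across the placebo and three levels of study drug dose".
- **Separate fits (SAP 13.3).** "Analyses will be stratified by each of the following subgroups": age, sex, frailty, surgical strata and surgical stress. A larger effect is expected in older patients, in frailer patients and after higher-stress procedures. No difference is expected by sex or surgical strata.
- **Significance rule (SAP 13).** "For all frequentist models, statistical significance will be defined as a one-sided p-value of <0.025". Subgroups are not excepted.
- **Multiplicity (SAP 13.6).** "No adjustment for multiple comparisons will be made, as the primary analysis model is for a single endpoint". The rest of that sentence covers secondary endpoints. Subgroups do not appear.
- **Exploratory status.** The non-inferential wording is in SAP 13.4, for exploratory and post hoc analyses, and is not tied to 13.3. SAP Section 9 treats the subgroups as prespecified.

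**The concern.** These are tests of the primary endpoint. Read together, Sections 13 and 13.3 attach a significance label to any within-level result that crosses 0.025, over many overlapping levels, and Section 13.6 gives no reason why that should go unadjusted. The trial stopped before its first interval analysis, so the overall result may be imprecise and a nominally significant level could draw attention it does not deserve.

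There is also a mismatch between question and method. A hypothesis that metformin works better in frail patients concerns the difference between frail and robust patients. Significance in one level and not in the other does not test that difference, and 13.3 names nothing that does.

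**Working it through.** The documents give no subgroup error rate, so there is no plan figure to reproduce.

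**1. Levels.** Listed: age 2 + sex 2 + frailty 2 + surgical strata 5 + stress 2 = 13. The no-operation level lies outside both populations, because SAP Section 8 requires surgery within 365 days. That leaves 12. Section 13.3 merges strata with 25 or fewer subjects; if the four usable strata become three or two, 11 or 10 levels remain.

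**2. Tests.** With three dose contrasts per level: 12 × 3 = 36 per population and 36 × 2 = 72 over ITT and PPA. With doses pooled: 12 and 24.

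**3. Reference values if tests were independent.** 1 − 0.975^k gives 26% for k = 12, 60% for k = 36 and 84% for k = 72. The tests share a placebo group, the factors overlap and PPA is nested in ITT, so these values are too high for the plan.

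**4. Simulation allowing for the correlation.** No effect of any dose in any level; the event is at least one one-sided p<0.025 in favour of metformin.
- From SAP Section 6: allocation √3:1:1:1. Since √3 + 3 = 4.732, placebo has 1.732/4.732 = 36.6% and each dose 1/4.732 = 21.1%.
- Assumed: N of 150 to 500 (4000 as a large-sample check); PPA a random 50-90% of ITT; age and sex split 50/50; unequal splits for frailty, stress and strata. Associating the factors with one another made almost no difference.
- Calibration: in the whole population, one pooled contrast was significant in about 2-3% of trials and at least one of three doses in about 6-7%, as expected.

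| Dose handling within each level | ITT | ITT and PPA |
|---|---|---|
| One pooled metformin contrast, 10-13 levels | 16-20% | 22-29% |
| Borrowing across dose, prior SD 0.5 | 26-28% | 33-37% |
| Borrowing across dose, prior SD 5 | 40% | 49-53% |
| Three separate contrasts, 12 levels | 40-43% | 49-57% |
| Same, tied HFD-like outcome, rank tests | 40-41% | 50-53% |
| Same, strata collapsed to three | 38% | 50% |
| Same, strata collapsed to two | 34% | 46% |
| Same, N = 150 with small-group rules | about 30-33% | about 36-38% |

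The 57% comes from a PPA share of 50%. The borrowing rows use a posterior probability above 0.975 as a stand-in, because the SAP gives no frequentist method of borrowing.

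**5. Why the small-group rules matter at low N.** SAP Section 11 does not model interventions with fewer than 10 subjects. Take N = 150, 35% frail and a 60% PPA share (both assumed). The frail level has 150 × 0.35 = 52.5 patients, or 52.5 × 0.211 = 11.1 per dose in ITT and 11.1 × 0.60 = 6.6 in PPA. Many PPA tests would drop out. At N = 300-500 the rules barely change the result (40-42% and 52-54%).

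**6. Which borrowing row applies.** SAP 13.1 prints 5² as the dose-prior variance and .5² for the parallel duration prior. The text was machine-read and the documents do not settle whether the two were meant to differ, so both rows are shown.

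**The case against.** A reader might infer a 40-55% chance that the trial falsely claims metformin works in some subgroup. The documents do not support that. No section says a claim follows from a subgroup p-value, and Section 13 gives primary inference to the Bayesian model. The upper figures also assume three separate dose tests, whereas 13.3 asks for borrowing, and they ignore the small-group rules when N is low. This objection stands, and it is why the result is a conditional range.

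A reader might also divide the figures by 2.5% and report a large multiple of the nominal level. That sets a chance over many tests against a per-test level. The SAP fixes no family-wise level for subgroups, so the ratio has no basis in the plan.

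Stating directions in advance, two of them as no difference, limits selective reading, and Protocol 10.5 calls its subgroups post-hoc. This helps only in part. The same Protocol section also calls them a priori, gives no error rule, and overlaps the SAP list only on surgical type. Protocol Section 7 expects the effect to depend on procedure type while SAP 13.3 expects no difference by strata, so a significant surgical stratum would bear on a stated hypothesis either way.

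None of this removes the Section 13 rule or supplies the missing interaction test.

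**Conclusion.** The concern holds as a gap in status and method. A stated rule would label within-level chance findings significant in about 10-12 levels and two populations, with no exploratory status, no interaction test and no coverage in 13.6.

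Under a global null, the chance of at least one nominally significant benefit is about 16-29% with doses pooled, about 26-37% with effective borrowing, and about 30-55% with three separate contrasts. The ranges rest on assumed N, subgroup shares and a random PPA subset. Dose handling moves the figure most; N matters mainly when it is low enough for the small-group rules to apply. Even the lowest scenario, 16%, is high enough that a lone significant level would be weak evidence.

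**What to change.** 1. **Section 13.3:** state that subgroup analyses are exploratory, that odds ratios with 95% confidence intervals will be shown for every level, and that no efficacy claim will rest on a subgroup.
2. **Section 13.3:** for each factor, add a treatment-by-subgroup interaction estimate with its interval, metformin versus placebo, and judge the directional hypotheses on that.
3. **Section 13:** exempt subgroup models from the p<0.025 rule.
4. **Section 13.6:** name the subgroups and say they are unadjusted because they are exploratory.

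The cost is SAP wording and one interaction term per factor; no new data are needed and the primary analysis is unchanged. The downside is that no subgroup result can be presented as statistically significant, and the interaction intervals are likely to be wide.

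SAP Section 5 holds unblinding only until the SAP is final, and Version 1 was finalised on 06 September 2023. The documents do not show whether unblinding has since occurred. If it has, apply the same label and interaction estimates in reporting.

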8.2.1. Inclusion Criteria for this Domain

Patients are eligible for this domain only if they have been scheduled for elective surgery at UPMC facilities and are being evaluated pre-operatively prior to surgery.

Other criteria include:

- Age \geq 60 years
- Age < 60 but evidence of comorbidity risk as represented by a Charlson Comorbidity Index of > 2 in 12 months prior to enrollment
- Able to take an oral medication in non-crushable pill form
- Women must be post-menopausal, which is defined as not having a menstrual period within the last 12 months

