## **6. INTERVENTIONS**

There is one active intervention and one control within this analysis plan:

- 1- Metformin
- 2- Placebo

Preoperative duration of study drug was pragmatically chosen based upon the time interval between the time of enrollment and scheduled operating room date including:

- 1- Short – 7-28 days
- 2- Medium – 29-90 days
- 3- Long – >90 days

Preoperative duration is not considered in the primary model but was considered in planned sensitivity analyses. Patients were randomly assigned,  $\sqrt{3}$ :1:1:1 to placebo and the 3 doses of metformin:

- 1- Placebo
- 2- Metformin 500mg ER
- 3- Metformin 1000mg ER
- 4- Metformin 1500mg ER

The dosing of and route of administration of metformin guidance included to take an oral dose once daily and complete all dispensed medication from the provided pill bottle.

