## 11. DESCRIPTIVE STATISTICS

All demographics, baseline characteristics, and perioperative information will be summarized for all randomized participants, the ITT, and PPA analysis populations. Summaries will be presented by treatment group (metformin vs placebo), by treatment and dosage group, and by surgical strata. Data abstracted prospectively throughout the trial, data within trial reporting documentation, as well as data abstracted from the electronic health record will be recorded and included in the summaries. Baseline demographics and characteristics will include age at randomization, sex at birth, race, ethnicity, body mass index, frailty status as measured by the Risk Analysis Index, smoking status, Charlson Comorbidity Index, occurrence of comorbid conditions, preoperative medications, ASA class, surgical strata, and year of randomization. All analyses will be completed both in the ITT and PPA populations.

Primary and supplemental tables will include the following populations:

- 1- By primary treatment group (Metformin vs placebo)
- 2- By primary treatment group, separated by dose
- 3- By primary treatment group, separated by preoperative duration and dose
- 4- By surgical strata

All endpoints will be modeled following a standard convention based upon the frequency of the events. For interventions with <10 subjects, we will summarize outcomes with No. (%) without modeling due to the small sample size. All analysis will be completed both in the ITT and PPA populations.

- 1- Ordinal endpoints will be summarized by the number and cumulative frequency of each outcome. The 25th, 50th, and 75th percentiles will be summarized.
- 2- Dichotomous endpoints will be summarized by the proportion in each category.
- 3- Composite endpoints will be summarized overall and for each component individually.
- 4- Time-to-event outcomes will be summarized by the 2.5th, 10th, 25th, 50th, 75th, 90th, and 97.5th percentiles from the Kaplan-Meier estimates, as available.
- 5- Continuous endpoints will be summarized by the mean, standard deviation or median, interquartile range (IQR) pending the distribution of the data.

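### SAP 13.3 examines its age and frailty hypotheses only through two-group splits fitted separately, with no interaction test and no use of age or the Risk Analysis Index on its own scale

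*SAP*

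**What the plan says.** SAP section 13.3 lists five subgroup factors for hospital free days at day 90. Two carry directional hypotheses about patient vulnerability:

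- Item 1: "Age >= overall median vs < overall median (hypothesis, more effective among those > median".
- Item 3: "Frailty, comparing robust/normal vs. frail/very frail (hypothesis, more effective among frail and very frail". The grouping "may be modified as necessary (e.g., to robust vs. normal/frail/very frail) if sample size for either group is <= 25".

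The method is a frequentist cumulative logistic model, and "Analyses will be stratified by each of the following subgroups". It keeps the primary analysis's handling of duration and dose. Section 13.3 writes no treatment-by-subgroup term, and no other section does so for age or frailty.

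Finer baseline data are listed. SAP section 11 includes age at randomization and "frailty status as measured by the Risk Analysis Index". Protocol section 10.5 adds a subgroup of patients eligible through comorbidity and not age. That subgroup is also categorical and is not among the five in SAP 13.3.

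**The concern.** Aging and frailty are the trial's stated rationale (SAP section 3), so these are the two effect modifiers a reader will look at first. The plan handles them in three ways that weaken the answer.

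- **Separate fits do not test the hypothesis.** A claim that metformin works better in one group than another is about the difference between two odds ratios. Two stratum-specific estimates leave the reader to judge that difference by eye.
- **Splitting discards order within each half.** A patient just under the age cut is treated like the youngest patient and unlike one just over the cut.
- **The frailty question is not fixed.** If a group has 25 or fewer patients, the cut may move, and the replacement is given only as an example.

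Information is already scarce, because the trial stopped before its first planned look at 500 patients (SAP section 4). Under SAP section 13.4, exploratory analyses after unblinding are not inferential. A continuous analysis therefore has to be specified beforehand to count as more than exploratory.

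**Working it through.** The documents give no power or information figure for the subgroup analyses, so there is nothing of the plan's own to reproduce.

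**Inputs from the documents**
- Test level for frequentist models: "statistical significance will be defined as a one-sided p-value of <0.025" (SAP section 13).
- Allocation (SAP section 6): √3 for placebo, then "1:1:1 to placebo and the 3 doses of metformin". Placebo share = √3/(√3+3) = 1.732/4.732 = 0.366; each dose = (1 − 0.366)/3 = 0.211.
- Age eligibility: 60 or over, or "Age < 60 but evidence of comorbidity risk as represented by a Charlson Comorbidity Index of > 2" (Protocol section 8.2.1).

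**Not in the documents, so assumed:** the age distribution, the Risk Analysis Index distribution, the frailty shares, the final N and the shape of the effect change.

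**Formula.** If the effect changes linearly with modifier X, the share of interaction information kept after splitting is the squared correlation between X and its two-group indicator. For normal X with share q in one group, this is φ(z_q)²/[q(1−q)].

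| Split (normal X) | Information kept | Lost | Sample-size factor |
|---|---|---|---|
| 50/50 | 0.3989²/0.25 = 0.637 | 36% | 1.57 |
| 75/25 | 0.3178²/0.1875 = 0.539 | 46% | 1.86 |
| 80/20 | 0.2800²/0.16 = 0.490 | 51% | 2.04 |

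**Power.** A continuous test with 80% power has an expected z of 2.80. After splitting, power = Φ(2.80√kept − 1.96), which gives 61%, 54% and 50%. A linear-model simulation (assumed N = 400, placebo share 0.366, assumed effect) gave 0.82 continuous against 0.60 for a median split, and 0.82 against 0.49 for 80/20. The drop depends on the starting point. From 20% power (expected z = 1.96 − 0.84 = 1.12), it falls only to about 14% or 12%.

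**Sensitivity to the assumed distribution**
- *Age, median split:* loss of 25% if uniform; about 34% if normal and truncated at 60; about 47–48% if 5–15% of patients are under 60; 52% if exponential above 60.
- *Frailty, normal index:* 57% at 85/15; 66% at 90/10. If the smaller group has just 26 patients, which does not trigger regrouping, the loss is 60% with N = 200 (13%) and 77% with N = 500 (5.2%).
- *Frailty as a four-level score 0–3:* about 20–33% at the planned cut and 29–64% at the example fallback, over illustrative shares. With equal shares, the variance is 1.25 and the covariance with the planned indicator is 0.25 × (0.5 + 1.5) = 0.5. Kept = 0.5²/(1.25 × 0.25) = 0.80, so 20% is lost.
- *True step at the median:* the split loses nothing. For normal X, it carries 1/0.637 = 1.57 times the information of the linear term.

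**Does the 25-patient rule secure a usable group?** A group of 26 has an expected 26 × 0.366 = 9.5 placebo patients and 26 × 0.211 = 5.5 per dose. SAP section 11 summarizes interventions with fewer than 10 subjects without modeling. If that applies within subgroups, a group can pass the 25-patient rule and still be too thin for dose effects.

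**The case against.** The case for leaving the plan alone has real content.

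- **The hypotheses are worded as group contrasts.** The SAP speaks of those above the median and of the frail and very frail. The losses above concern a gradient. This stands as a limit on the figures. However, the age cut is wherever this sample's median falls, so a true step exactly there is unlikely, and even the group contrast has no planned test.
- **The regrouping is blind to outcome.** It is triggered by group size, and SAP section 5 delays unblinding until the SAP is final. A reader might infer a data-driven choice of the favorable cut. The documents do not support that: the rule leaves the cut undetermined but does not tie it to results. Naming one fallback cut would cure this part alone.
- **A linear age term has its own weakness.** Patients under 60 enter only through comorbidity, so the young end of the age scale is a selected group with leverage on the slope. A spline shows curvature but does not remove that selection. This stands, and the fix has to deal with it.
- **The practical gain may be small.** With low starting power, either analysis will often miss a real difference. That is fair, but it is no reason to use the less informative analysis when the data are already available.

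**Conclusion.** The concern holds as a cheap improvement. SAP 13.3 addresses its directional age and frailty hypotheses only by stratified fits in two-group splits. The age cut depends on the sample, and the fallback frailty cut is open. No interaction test is planned, and neither modifier is used on its own scale.

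The size is conditional. The loss is about 36% for a median split, given a normal modifier and a linear change in effect on the log-odds scale. It is about 51% if, in addition, frailty happens to split 80/20. A reader might take 36–51% as a property of this plan. The documents do not support that, because they give no age distribution, index distribution or frailty shares. The age criteria themselves make a normal age distribution doubtful. Plausible losses run from about 20% to over 70%, with none if the effect steps at the cut.

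Nor does this point cast doubt on the primary analysis in SAP 13.1, which it does not touch.

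**What to change.** In SAP section 13.3, for items 1 and 3:

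1. Make the inferential analysis one proportional odds model on the full analysis population, adjusted for surgical strata, with pooled treatment (metformin vs placebo) × age in years. Fit a second such model with pooled treatment × Risk Analysis Index score, or the ordered four-level category if only that is available. Report the interaction estimate with its interval. State that treatment is pooled here, since 13.3 otherwise carries over the primary analysis's dose structure.
2. Check linearity with a spline term.
3. Repeat the age model in patients aged 60 or over, because younger patients enter only through comorbidity.
4. Keep the two-group odds ratios for the forest plot, and replace the open-ended regrouping wording with one fixed fallback frailty cut.

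If unblinding has already occurred, label these models exploratory, in line with SAP section 13.4.

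The cost is a paragraph of SAP text and a few extra model fits on baseline data the SAP already lists. The downside is reliance on linearity, which steps 2 and 3 examine but cannot guarantee.
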